14.0 STATISTICAL SOFTWARE

Statistical analyses will be performed using version 9.3 (or newer) of SAS on a Linux operating system.

15.0 DATA HANDLING CONVENTIONS

15.1 SUMMARY STATISTICS

The following statistical summaries will be presented for each type of data. Further details are specified in the tables, figures, and listings shells.

- Continuous variables will be summarized by descriptive statistics (number of patients, mean, standard deviation (SD), median, Q1, Q3, minimum, and maximum values).
- Categorical variables will be summarized by frequency distributions (counts and percentages).
- The results for ocular related assessments in the fellow eye will be summarized across the treatment groups, if applicable.

15.2 VISIT TIME WINDOWS

[Table 15.2–1](#) presents the visits assigned for efficacy and safety analyses and the corresponding range of treatment days (window) during which an actual visit may occur.

Table 15.2–1. Visit Time Windows

Derived Visit	Scheduled Visit (Target Day^a)	Window
Baseline	Day -45 to 0	Days < 0
Day 0	Treatment Visit (Day 0)	Day 0
Day 1	Post Injection Visit (Day 1)	Day 1
Day 7	Day 7 (7)	Days (2, 12)
Month 1	Month 1 (30)	Days (13, 47)
Month 3	Month 3 (91)	Days (48, 135)
Month 6	Month 6 (183)	Days (136, 230)
Month 9	Month 9 (274)	Days (231, 317)
Month 12	Month 12 (365)	Days (318, 412)
Month 18	Month 18 (548)	Days (413, 682)
Month 24	Month 24 (731)	Days (683, 778)
Month 36	Month 36 (1096)	Days (779, 1413)
Month 48	Month 48 (1461)	Days (1414, 1508)
Month 60	Month 60 (1826)	Days (1509, 2144)

Month 72	Month 72 (2192)	Days (2145, 2238)
Month 84	Month 84 (2557)	Days (2239, 2874)
End of study ^b	Final or Termination Visit	

a Relative to the date of the first dose of study treatment. Day 0 = the date of the first dose of study treatment.

b Presented in summary tables for all visit-based parameters.

If the assessment date (if the assessment date is unavailable, use visit date instead) is on or after the date of the first dose of study treatment, the study day is calculated by assessment date – date of the first dose of study treatment + 1. If the assessment date is before the date of the first dose of study treatment, the study day is calculated by assessment date – date of the first dose of study treatment. Therefore, a negative day indicates a day before the start of the study treatment.

If a patient has 2 or more visits within the same window, the last visit with a non-missing value will be used for analysis.

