## 5 Study Assessments and Intravitreal Injection

Patients diagnosed with advanced RP and who are eligible based on inclusion and exclusion criteria will be invited to participate in this study. After obtaining informed consent and authorization, patients will undergo a complete physical examination and laboratory testing to assess eligibility for the study.

Patients who meet inclusion criteria will be considered eligible for study entry and will receive a single intravitreal injection of RST-001. Following RST-001 administration (Day 0) patients will be assessed on the first post injection day (Day 1).

The visit schedule includes:

- Core study visits: Twelve visits are planned over 24 months, including Screening and Baseline visits, Day 0, Day 1, Day 7, and Months 1, 3, 6, 9, 12, 18, and 24.
- Long-term follow-up: After completion of the Month 24 visit, each patient will participate in a long-term follow-up study for a total of an additional 3 years. These visits include yearly office visits for 3 years (Months 36, 48, and 60).

Core study visits are described in [Table 2](#) and long-term follow-up visits are described in [Table 3](#).

Study visits may be impacted due to the COVID-19 pandemic. This may include changes such as telephone or virtual visits, visits at alternative locations, or changes in the visit frequency and timing of study procedures, among others. Additional details are provided in the subsequent section. Every effort is to be made to ensure the safety of subjects and site staff, while maintaining the integrity of the study. If visits cannot be conducted onsite due to travel restrictions or other pandemic-related reasons, follow the updates below on how to proceed.

During the COVID-19 pandemic, if it is not possible for all study procedures to be performed as specified due to travel restrictions or other reasons, the following modifications are allowed with agreement from the sponsor:

- If permitted by local regulations, the IRB/IEC, and the subject, postbaseline visits may be conducted virtually.
- Study Visits and/or activities are to be performed as scheduled whenever possible.

**Table 2** Study Visit Schedule: Core Study Visits

	Screening b	Baseline b	Day			Month					
			0	1	7 ± 1	1 ± 7	3 ± 7	6 ± 7	9 ± 7	12 ± 30	18 ± 30
Visit Windows (Days) a	-45 to -8	-7 to -1	0	1	7 ± 1	1 ± 7	3 ± 7	6 ± 7	9 ± 7	12 ± 30	18 ± 30
Informed Consent/Authorization	X										

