15.3 DERIVED VARIABLES

Analyses visits will be derived per Section 15.2. Observed data will be used for the primary and secondary objectives without derivation.

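### SAP 15.2 numbers the dosing date two ways (Day 0 in the table, study day 1 by the formula), and the formula as written puts the Day 0 and Day 1 visits in the wrong windows

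*SAP*

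**What the plan says.** SAP 15.2 gives two numberings.

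- **The table.** Footnote a to Table 15.2-1 states "Day 0 = the date of the first dose of study treatment". The treatment visit has Day 0 as its whole window, the post-injection visit has Day 1 as its whole window, and the Day 7 window runs from day 2 to day 12.
- **The text below the table.** For an assessment on or after the first-dose date, "the study day is calculated by assessment date – date of the first dose of study treatment + 1". For an earlier assessment, nothing is added.

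The same section settles multiple visits in one window: "If a patient has 2 or more visits within the same window, the last visit with a non-missing value will be used for analysis".

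SAP 15.3 makes this section operative: "Analyses visits will be derived per Section 15.2". Its next sentence reads "Observed data will be used for the primary and secondary objectives without derivation". What that means is unclear, and it does not say which day convention applies.

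Protocol section 5 uses the table's convention: administration is on Day 0, and Day 1 is the first day after the injection.

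**The concern.** With the formula as written, study day runs −2, −1, 1, 2 and never takes the value 0, yet the table has a row whose only window is Day 0. The section does not say which numbering prevails.

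The early visits are where a one-day shift does damage, because the Day 0 and Day 1 windows are a single day wide. Protocol 5.2.16 measures study-eye IOP before and after the injection on Day 0, and IOP in both eyes at every other visit. SAP 11.4 summarises IOP and its change from baseline at each visit. If those summaries use windows built from the formula, treatment-day pressure would appear as next-day pressure. The real next-day pressure would drop out for every patient with a Day 7 value. In a first-in-human intravitreal study, those two time points answer different safety questions.

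The cup/disc ratio, also summarised by visit in SAP 11.4, may be affected in the same way, since protocol 5.2.15 calls for an ophthalmic examination at each post-treatment visit. The other assessments at Days 0, 1 and 7 cannot be read in the public schedule.

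**Working it through.** **Inputs.** The windows come from SAP Table 15.2-1. Visit tolerances come from protocol Tables 2 and 3: Day 7 ± 1 day, Months 1 to 9 ± 7 days, Months 12 and 18 ± 30 days, Months 36 to 60 ± 30 days. The Month 24 tolerance is not legible in Table 2, so ± 30 days is assumed.

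**Method.** Let *e* be elapsed days, assessment date minus first-dose date. For *e* ≥ 0 the formula gives study day *e* + 1, and footnote a gives day *e*. Each scheduled visit was mapped to a window both ways.

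| Scheduled visit | *e* | *e* + 1 | Window by formula | Window by footnote a |
|---|---|---|---|---|
| Day 0 | 0 | 1 | **Day 1** | Day 0 |
| Day 1 | 1 | 2 | **Day 7** (2–12) | Day 1 |
| Day 7 | 6–8 | 7–9 | Day 7 (2–12) | Day 7 |
| Month 1 | 23–37 | 24–38 | Month 1 (13–47) | Month 1 |
| Month 6 | 176–190 | 177–191 | Month 6 (136–230) | Month 6 |
| Month 24 (assumed ± 30) | 701–761 | 702–762 | Month 24 (683–778) | Month 24 |
| Month 60 | 1796–1856 | 1797–1857 | Month 60 (1509–2144) | Month 60 |

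Months 3, 9, 12, 18, 36 and 48 also stay in their own windows both ways. The formula therefore misassigns 2 of 13 scheduled visits, and footnote a misassigns 0 of 13. From Day 7 on, the tightest upper margin under the formula is 12 − 9 = 3 days, at Day 7, so no later scheduled visit moves.

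**What happens to the Day 1 value.** Under the formula it shares the Day 7 window with the Day 7 visit. The last non-missing visit is used, so Day 7 replaces it. If the Day 7 value is missing, the Day 1 value is reported as Day 7.

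**Off-schedule visits.** Adding 1 changes the window only on the last day of a window, so there is one such day per row from Day 0 on.

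- Through the Month 60 row ("Days (1509, 2144" in the table) there are 13: elapsed days 0, 1, 12, 47, 135, 230, 317, 412, 682, 778, 1413, 1508 and 2144.
- Through the Month 84 row ("Days (2239, 2874") there are 15, adding 2238 and 2874.

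Only days 0 and 1 lie inside a protocol visit window.

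**Which convention the table was built on.** Months × 30.4375, rounded half up, gives 30, 91, 183, 274, 365, 548, 731, 1096, 1461, 1826, 2192 and 2557. For example, 6 × 30.4375 = 182.6, which rounds to 183, and 24 × 30.4375 = 730.5, which rounds to 731. All 12 monthly target days match with no 1 added. With 1 added, none match.

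**The case against.** The best case for leaving the text alone is that the table already carries its own scale. The sentence introducing it speaks of treatment days, footnote a fixes that scale at Day 0 for dosing, and the formula defines a differently named quantity, study day. The row labels, target days and protocol visit names all favour the footnote. A programmer who coded the formula would find the Day 0 row unreachable and its column empty for every patient. The consequence is also small: a few descriptive summaries, about three patients per dose group in Phase 1, every assessment in the listings (SAP 15.4), and dose-escalation and stopping decisions that do not depend on this table. Finally, SAP 4.0 puts the output specifications in a separate document, which may tabulate Day 0 IOP by pre- and post-injection time point and not by derived window.

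Much of this stands. The footnote is the more natural reading, an empty column might well be noticed, and the IOP effect depends on specifications not seen here. It does not remove the conflict. Treatment day has no formula of its own, the only formula sits in the windowing section, and SAP 15.3 sends analysis visits to that section. The SAP does not say that nominal visit labels are used instead, and its text should not depend on someone noticing an empty column.

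**Conclusion.** The contradiction is real, and the misassignment follows directly from the formula as written: 2 of 13 scheduled visits, affecting the Day 0 and Day 1 columns for all dosed patients (up to about 21). Two conditions apply. The formula must be used literally for windowing, and the early by-visit summaries must be built from the derived windows. If footnote a is programmed, no error arises.

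The damage is confined to early by-visit summaries: IOP, and possibly cup/disc ratio. On-schedule Month 6 primary measures, adverse event tables and data listings are untouched. Scheduled visits from Day 7 on keep their windows, although the Day 7 window would also receive the stray Day 1 records. The text should be corrected before the analysis is programmed, but the point does not threaten the primary result.

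**What to change.** In SAP 15.2, define study day for visit windowing as assessment date minus first-dose date for all records, which means deleting the added 1. This agrees with footnote a, the protocol visit names and all 12 monthly targets. If a count starting at 1 is needed elsewhere, give it a separate name and state that it is not used for windows. Keeping the added 1 and moving the Day 0 row, the Day 1 row and the start of the Day 7 window up by one would also remove the conflict, but the table would then disagree with the protocol's visit names.

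The cost is one sentence in the SAP, a check of the visit-window derivation, and a check of the separate table and listing specifications for other uses of study day. As an editorial matter, the Baseline row could cite the baseline definition in SAP 11.0.

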11.3 SECONDARY OCULAR SAFETY MEASUREMENTS

The following ocular safety measures (excluding the primary safety endpoints at 6 months as described in Section 11.2) and their change from baseline values will be listed and summarized by visit and by treatment group separately in each phase. Data collected from the extended follow-up will be included in data listings.

- Change in visual acuity in the study eye from Baseline (defined as last observed value prior to dosing) to [REDACTED]
- Change in full field sensitivity in the study eye from Baseline to [REDACTED]
[REDACTED]
- Change in ambulation scores from Baseline to [REDACTED]
- Change in object detection and discrimination scores from Baseline to [REDACTED]
[REDACTED]
- Change in VEP and ERG scores from Baseline to [REDACTED]
- Anatomical parameters as measured in the study eye by:
 - Fundus photography - Qualitative assessment of the change in retinal appearance from Baseline to [REDACTED]
 - Spectral domain-OCT (SD-OCT) - Qualitative assessment of the change in retinal cross-sectional appearance from Baseline to [REDACTED]
[REDACTED]

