11.4 OTHER OCULAR SAFETY MEASUREMENTS

Other ocular safety measurements include the following assessments during the core study visits and clinic visits of the long-term follow-up visits:

- IOP measurements in the study eye (other assessment at month 6 which is the primary endpoint)
- Findings in the study eye from ocular biomicroscopic examination (Table 11.4-1)
- Findings in the study eye from ophthalmoscopy examination (Table 11.4-2)

Table 11.4–1. Findings and Severity from Ocular Biomicroscopic Examination

Biomicroscopic Eye Area	Findings	Severity^a
Eyelids/eyelid margins/lashes	Erythema Edema Crusting Other	+0.5 (Trace) +1 (Mild) +2 (Moderate) +3 (Severe) Not Applicable
Conjunctiva (bulbar or palpebral)	Hyperemia Edema Subconjunctival Hemorrhage Discharge Blanching Follicles Pterygium, encroaching on visual axis Pterygium, not encroaching on visual axis Other	+0.5 (Trace) +1 (Mild) +2 (Moderate) +3 (Severe) Not Applicable
Cornea: • Central Cornea • Peripheral Cornea • Central and Peripheral Cornea	Punctate Epithelial Staining Filaments Infiltrates Edema Corneal Guttata Endothelial Pigment Keratic Precipitates Neovascularization Opacity/Opacities Stromal Haze Other	+0.5 (Trace) +1 (Mild) +2 (Moderate) +3 (Severe) Not Applicable
Anterior chamber	Cells Flare Anterior Synechiae Hypopyon, Details and Levels (mm) Hyphema, Details and Levels (mm) Other	0 (<1 cell, None) +0.5 (1-5) +1 (6-15, Faint) +2 (16-25, Moderate) +3 (26-50, Marked) +4 (>50, Intense (including fibrin)) Not Applicable
Iris/pupil	Rubeosis Iridis, anterior chamber angle involved Rubeosis Iridis, anterior chamber angle not involved Afferent Pupillary Defect (APD) Other	Not Applicable

^aSeverity for Anterior chamber cells and flare are included before or after '/', respectively.

Table 11.4–2. Findings and Severity from Ophthalmoscopy Examination

Ophthalmoscopy Eye Area	Findings	Severity^a
Optic Nerve	Cup/Disc Ratio (Value range 0.0 - 1.0)	Not Applicable
Vitreous	Cells Vitreous Haze Vitreous Hemorrhage Posterior Vitreous Detachment Other	+0.5 (None, No Haze) +1 (Minimal, Trace) +2 (Mild, 1+) +3 (Moderate, 2+) +4 (Marked, 3+) +5 (Severe, 4+) Not Evaluable Not Applicable
Optic Nerve	Disc Hemorrhage Other	Not Applicable
Macula	Intraretinal Fluid Subretinal Fluid Intraretinal Hemorrhage Subretinal Hemorrhage Rhegmatogenous Detachment Tractional Detachment Pigment Epithelial Detachment Other	Not Applicable
Fundus	Other	Not Applicable

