Retina Periphery	Retinal Hemorrhage Retinal Tear Rhegmatogenous retinal detachment, macula center attached Rhegmatogenous retinal detachment, macula center detached Tractional retinal detachment, macula center attached [Tractional retinal detachment, macula center detached Exudative retinal detachment, macula center attached Exudative retinal detachment, macula center detached Other retinal detachment Round (Atrophic) Retinal Hole Lattice Degeneration Other	Not Applicable

^aSeverity for Vitreous flare and Vitreous Haze are included before or after ' ; ' , respectively.

The findings from both ocular biomicroscopic and ophthalmoscopy examinations with prespecified terms will be coded using MedDRA, version 21.0 or newer.

Descriptive statistics for IOP measurements and changes from the baseline values at each visit will be presented by treatment group separately for each phase.

Similarly, descriptive statistics for cup/disc ratio measurements from ophthalmoscopy examination and changes from the baseline values at each visit will be presented by treatment group separately for each phase.

The number and percent of patients with more than one grade increase from baseline for any findings will be summarized by preferred term and by treatment group separately for each phase.

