15.4 REPEATED OR UNSCHEDULED ASSESSMENTS OF SAFETY PARAMETERS

If a patient has repeated assessments before the start of the first treatment, the results from the final non-missing assessment made prior to the start of the study treatment will be used as baseline. If end-of-study assessments are repeated or if unscheduled visits occur, the last non-missing Post-treatment assessment will be used as the end-of-study assessment for generating summary statistics. However, all Post-treatment assessments will be used for PCS value determinations, and all assessments will be presented in the data listings.

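### From Month 12 to Month 60 the SAP's visit windows do not fit its own target days, so off-schedule visits can empty or overwrite by-visit cells; the study-day formula also misplaces the Day 1 visit

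*SAP*

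**What the plan says.** SAP Table 15.2-1 gives each derived visit a target day and a range of study days. The ranges are contiguous, but their widths alternate: Month 48 is "Days (1414, 1508" and Month 60 is "Days (1509, 2144" (closing brackets left off). SAP 15.2 states no rule for setting the limits and gives no reason for the alternation. SAP 15.3 confirms that analysis visits are derived this way.

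Where a range holds several records, SAP 15.2 says: "If a patient has 2 or more visits within the same window, the last visit with a non-missing value will be used for analysis". SAP 15.4 adds a rule for one other row only: "if unscheduled visits occur, the last non-missing Post-treatment assessment will be used as the end-of-study assessment". It also keeps all post-treatment values for the potentially-clinically-significant flags and the listings. It does not say how unscheduled visits are treated in the ordinary by-visit rows.

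Footnote a of the table makes the dosing date Day 0. The text below the table computes study day, for dates on or after dosing, as the date difference plus 1.

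The protocol allows 30 days either side at Months 12 and 18 (Table 2) and at Months 36, 48 and 60 (Table 3). Its pandemic text in Section 5 foresees "changes in the visit frequency and timing of study procedures", while asking for visits as scheduled whenever possible.

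**The concern.** Visits with the same protocol tolerance get analysis windows of 95, 270 or about 635 days. A visit made between two targets can therefore be reported under the more distant one. Combined with the last-record rule, it can displace a value that was measured on time.

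The tables at risk are the by-visit ones. In the core study these are the SAP 10 efficacy summaries and the SAP 11.3 and 11.4 ocular summaries. After Month 24 the reach is narrower:

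- SAP 11.3 says of its measures: "Data collected from the extended follow-up will be included in data listings".
- SAP 11.4 does extend to the long-term clinic visits ("Other ocular safety measurements include the following assessments during the core study visits and clinic visits of the long-term follow-up visits") and says: "Descriptive statistics for IOP measurements and changes from the baseline values at each visit will be presented". Cup/disc ratio is treated the same way. Increases in examination grade are counted by preferred term and group, with no split by visit.
- Visual acuity is collected at Months 36, 48 and 60 (Protocol Table 3), and SAP 10 summarises it by visit.

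So after Month 24 the by-visit effect concerns visual acuity, IOP and cup/disc ratio. Groups are small: one displaced record is 1 of about 3 patients in a Phase 1 dose group, or 1 of 6 to 12 in Phase 2a.

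**Working it through.** **Inputs.** Targets and windows come from SAP Table 15.2-1, tolerances from Protocol Tables 2 and 3. The Month 24 column is cut off in the text available to me. I assume ±30 days, which the Amendment 1 summary (Protocol 20.3) also records.

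**Step 1: distance from target to each limit.**

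| Visit | Target | SAP window | Days before/after | Width | Protocol |
|---|---|---|---|---|---|
| Month 12 | 365 | 318–412 | 47/47 | 95 | ±30 |
| Month 18 | 548 | 413–682 | 135/134 | 270 | ±30 |
| Month 24 | 731 | 683–778 | 48/47 | 96 | ±30 (assumed) |
| Month 36 | 1096 | 779–1413 | 317/317 | 635 | ±30 |
| Month 48 | 1461 | 1414–1508 | 47/47 | 95 | ±30 |
| Month 60 | 1826 | 1509–2144 | 317/318 | 636 | ±30 |

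**Step 2: printed limits against midpoints of adjacent targets.** The printed limit is taken halfway between the last day of one window and the first day of the next.

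| Pair | Midpoint | SAP limit | Gap | Days affected |
|---|---|---|---|---|
| 12/18 | (365+548)/2 = 456.5 | 412.5 | 44 | 413–456: nearest 12, labelled 18 |
| 18/24 | (548+731)/2 = 639.5 | 682.5 | 43 | 640–682: nearest 24, labelled 18 |
| 24/36 | (731+1096)/2 = 913.5 | 778.5 | 135 | 779–913: nearest 24, labelled 36 |
| 36/48 | (1096+1461)/2 = 1278.5 | 1413.5 | 135 | 1279–1413: nearest 48, labelled 36 |
| 48/60 | (1461+1826)/2 = 1643.5 | 1508.5 | 135 | 1509–1643: nearest 48, labelled 60 |

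The total is 44 + 43 + 135 + 135 + 135 = 492 days: 44 + 43 = 87 up to Day 778 and 3 × 135 = 405 after it. If the targets are read as elapsed days and the plus-1 formula is applied, the total is 493.

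**Step 3: is nearest target a fair yardstick?** The SAP does not state it, but the limits between Months 3 and 12 follow it closely: 135.5 against 137, 230.5 against 228.5, and 317.5 against 319.5, all within 2 days. By the same yardstick the Day 7/Month 1 limit is off by 6 days (12.5 against 18.5) and the Month 1/3 limit by 13 (47.5 against 60.5).

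**Step 4: apply the rules to single visits, all others on target.**

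- *Empty cell, caused by the limits.* A Month 12 visit on Day 430 is labelled Month 18, a Month 24 visit on Day 800 is labelled Month 36, and a Month 48 visit on Day 1520 is labelled Month 60. Each leaves its own visit empty. It drops out of the table once the later visit has a value.
- *Empty cell and replacement, the latter caused by the last-record rule.* A Month 24 visit on Day 670 becomes the Month 18 value in place of Day 548. A Month 48 visit on Day 1400 becomes the Month 36 value in place of Day 1096.
- *Early termination or unscheduled visit on Day 660.* It is 731 − 660 = 71 days from Month 24 and 660 − 548 = 112 from Month 18, yet it replaces the Month 18 value.

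The thresholds are 48 days late for Month 12, 49 early or 48 late for Month 24, and 48 early or late for Month 48. For Months 12 and 48 that is 48 − 30 = 18 days beyond the protocol window.

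**Step 5: on-time visits.** Every day in each protocol window from Day 7 to Month 60 receives its own label (for example Month 12, Days 335–395 inside 318–412), with or without the plus 1.

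**Step 6: study day.** With the plus 1, the dosing date is 0 + 1 = 1, so it falls in the Day 1 row and the Day 0 row can never be filled. The visit one day after dosing is 1 + 1 = 2, which falls in the Day 7 window of Days 2 to 12.

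**Step 7: Month 6.** The limits are sound. The last-record rule still lets a repeat assessment up to Day 230 replace the scheduled one. The protocol limit is 183 + 7 = Day 190, so that is 40 days beyond it.

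**The case against.** The SAP never promises nearest-target labels. Its windows have no gaps and contain every protocol window from Day 7 on. The 492 is a count of calendar days, not of visits or data. Harm needs a scheduled visit some 48 or more days off target, or an extra or termination visit in a particular gap, and the documents give no frequency for either. The summaries are descriptive, the listings hold every record, and an early-termination value also appears in the End of study row. A last-record rule is a legitimate prespecified choice, and a last record may follow resolution as easily as a problem. SAP 10 speaks of scheduled visits, so it is arguable whether unscheduled records enter its rows.

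Most of this stands and sets the severity. It does not explain why equal tolerances receive such unequal windows. The multiple-visit rule in SAP 15.2 applies to efficacy and safety alike and makes no exception for unscheduled visits. The replacement by an early Month 24 or 48 visit needs no unscheduled record at all.

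A reader might infer more than the documents support:

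- *That the last-record rule empties cells.* It does not. The limits do so under any selection rule, and a late Month 12, 24 or 48 visit does not displace the next visit's value when that visit has data.
- *That all long-term outcomes are affected.* Examination grade increases have no by-visit split, and SAP 11.3 measures are only listed after Month 24.
- *That the Month 6 limits are wrong.* They lie within 2 days of the midpoints. The point there concerns the selection rule and is secondary.

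**Conclusion.** The concern holds. The limits from Month 12 to Month 60 are inconsistent with the table's own targets by 44, 43, 135, 135 and 135 days. If followed as written, they can leave Month 12, 24 or 48 empty and, with the last-record rule, replace real Month 18 or 36 values. The plus-1 formula contradicts footnote a and misplaces even an on-time Day 1 visit.

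Severity is minor to moderate. The size rests on nearest target as the standard and on ±30 days at Month 24. It would be too strong to conclude that on-time visits from Day 7 are mislabelled or that the trial's safety conclusion is at risk: Step 5 shows the former is not so, and the criterion of no related grade 3 or greater adverse event (SAP 5.0) does not use these windows.

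**What to change.** 1. Drop the plus 1 so that the dosing date is Day 0, as footnote a says.
2. Use contiguous midpoint windows: Day 7, 2–18; Month 1, 19–60; Month 3, 61–137; Month 6, 138–228; Month 9, 229–319; Month 12, 320–456; Month 18, 457–639; Month 24, 640–913; Month 36, 914–1278; Month 48, 1279–1643; Month 60, 1644 and later. No day between the Month 12 and Month 60 targets is then labelled with a visit other than the nearest. The Day 7, Month 1 and Month 3 changes correct the 6- and 13-day offsets.
3. Within a window, use the non-missing record of the scheduled visit it belongs to, otherwise the record closest to target. Early-termination and unscheduled records then cannot override a scheduled value, at Month 6 included; termination values stay in the End of study row.
4. Flag records outside the protocol window, and delete the Month 72 and 84 rows, which the current protocol no longer has.

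The cost is one table edit and reprogramming of one derivation. The SAP still follows Amendment 2 and so needs revision anyway, and Protocol 11.3.6 has the analysis plan finalised before database lock. The downside is small: yearly windows stay wide (Month 24 −91/+182, Months 36 and 48 ±182), so far-off visits still take the nearest label and depend on the flag.
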